### 6.2.5. Subgroup Analysis of the Primary Endpoint

Subgroup analysis comparing each filgotinib dose groups to the MTX alone group will be performed at Week 24 for the primary endpoint in the subgroups specified in Section 3.4.

The proportion of subjects who achieve ACR20 will be analyzed using the Fisher’s exact test based on the NRI method for comparison between treatment groups. The number and percentage of subjects with ACR20 will also be provided for each treatment group within the subgroups.

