### **3. GENERAL CONSIDERATIONS FOR DATA ANALYSES**

Analysis results will be presented using descriptive statistics. For categorical variables, the number and percentage of subjects in each category will be presented; for continuous variables, the number of subjects (n), mean, standard deviation (SD) or standard error (SE), median, first quartile (Q1), third quartile (Q3), minimum, and maximum will be presented.

All statistical tests will be 2-sided and performed at the 5% significance level unless otherwise specified.

By-subject listings will be presented for all subjects in the All Randomized Analysis Set and sorted by subject identification (ID) number, visit date, and time (if applicable). Data collected on log forms, such as AEs, will be presented in chronological order within the subject. The treatment group to which subjects were randomized will be included in the listings, as well as age, sex at birth, race, and ethnicity.

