### 3.4. Examination of Subject Subgroups

The primary and key secondary efficacy endpoints will be examined using the following subgroups (but not limited to the ones listed below):

- Age (on the first dosing date of any study drug, < 65 or ≥ 65)
- Sex at birth (male, female)
- Race
- Baseline weight ( < 60 kg, ≥ 60 to < 100 kg, ≥ 100 kg)
- Geographic region (A, B, C, or E)
- Presence of RF or anti-CCP Ab (Yes or No)
- Duration of RA diagnosis on the first dosing date of any study drug (< 1 year, ≥ 1 to < 2 years, ≥ 2 years)
- Disease activity at Baseline (DAS28[CRP] ≤ 5.1 or DAS28[CRP] > 5.1)
- Concurrent use of oral systemic corticosteroids on the first dosing date of any study drug (Yes or No)
- High-sensitivity C-reactive protein (hsCRP) at baseline (≥ 4 mg/L, < 4 mg/L)

Lists of oral systemic corticosteroids are provided in [Appendix 1](#).

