### **6.2.3. Primary Analysis of the Primary Efficacy Endpoint**

To test for superiority of filgotinib 200 mg in combination with MTX group versus MTX alone group in proportion of subjects who achieve ACR20 at Week 24, a logistic regression analysis with treatment groups and stratification factors in the model will be used. Subjects who do not have sufficient measurements to establish efficacy at Week 24 will be considered as failures (ie, NRI). The p-value from the logistic regression model for testing the superiority of filgotinib 200 mg in combination with MTX as compared to MTX alone will be provided. The 2-sided 95% confidence interval (CI) of the ACR20 response rate at Week 24 based on normal approximation for each treatment group will be provided for each treatment group. In addition, non-stratified ACR20 response rate difference between treatment groups with its 95% CI based on the normal approximation will be provided.

The comparisons of other filgotinib dose groups versus MTX alone group in proportion of subjects achieving ACR20 at Week 24 will also be conducted with the similar logistic regression model with NRI.

The number and percentage of ACR20 nonresponders observed and nonresponders due to missing at Week 24 will be summarized respectively by treatment groups.

For subjects with observed ACR20 outcomes (ie, responders and observed nonresponders) at Week 24, actual values and change from Baseline at Week 24 in individual components, including TJC68, SJC66, SGA, PGA, Subject's Pain Assessment, and hsCRP, will be summarized by using descriptive statistics (sample size, mean, SD, median, Q1, Q3, minimum, and maximum) by treatment groups.

The proportions of subjects achieving ACR20 (using NRI) will be plotted over time by treatment.

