#### **6.3.4. Subgroup Analysis of Key Secondary Endpoints**

Subgroup analysis comparing each filgotinib dose groups to the MTX alone group will be performed at Week 24 for the key secondary efficacy endpoint in the subgroups specified in Section 3.4.

The subgroup analysis for the proportion of subjects with DAS28(CRP) < 2.6 will be performed using the Fisher's exact test based on the NRI method. The number and percentage of subjects with DAS28(CRP) < 2.6 will also be provided for each treatment group within the subgroups

The change from Baseline in HAQ-DI will be analyzed using the MMRM method with baseline value, treatment, visit, and treatment by visit interaction included as fixed effects and subjects being the random effect. The LS mean, LS mean difference, SE, and 95% CI will be presented. The change from Baseline in mTSS, change from Baseline in SF-36 PCS and change from Baseline in FACIT-Fatigue will be analyzed similarly using the MMRM model, respectively. Descriptive statistics for actual values and change from baseline will also be presented for each treatment group within the subgroups.

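### By subgroup, ACR20 and DAS28(CRP) < 2.6 get only a within-level Fisher p-value: no rate difference, no confidence interval and no test of whether the effect differs between levels

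*SAP*

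**What the plan says.** SAP 3.4 states that "The primary and key secondary efficacy endpoints will be examined using the following subgroups" and lists ten factors as an open list. Leaving out race, whose categories are not given, these make 22 levels.

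- **ACR20 (SAP 6.2.5).** The method is Fisher's "exact test based on the NRI method for comparison between treatment groups". The only other output is descriptive: "The number and percentage of subjects with ACR20 will also be provided for each treatment group within the subgroups".
- **DAS28(CRP) < 2.6 (SAP 6.3.4).** "The subgroup analysis for the proportion of subjects with DAS28(CRP) < 2.6 will be performed using the" Fisher's "exact test based on the NRI method", again with number and percentage per arm.
- **HAQ-DI, mTSS, SF-36 PCS and FACIT-Fatigue (SAP 6.3.4).** The method is an MMRM within subgroup. For HAQ-DI "The LS mean, LS mean difference, SE, and 95% CI will be presented", and the other three are handled similarly.
- **ACR20 in the whole FAS (SAP 6.2.3).** Besides the logistic regression p-value, a "non-stratified ACR20 response rate difference between treatment groups with its 95% CI based on the normal approximation will be provided".

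The only interaction term anywhere in the SAP is treatment by visit. Section 8 of the protocol describes no subgroup analysis. SAP section 3 sets the general level: "All statistical tests will be 2-sided and performed at the 5% significance level unless otherwise specified".

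**The concern.** A subgroup analysis asks whether the treatment effect is consistent across levels of a factor. A p-value computed inside one level asks whether there is evidence of any effect there, and its answer depends heavily on how many patients the level holds. Comparing a significant level with a non-significant one is not a test of a difference between them.

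For the two binary endpoints, one of them primary, the p-value is the only inferential output planned. A small level with a non-significant result would therefore be tabulated without an estimate and interval to show whether it is compatible with the overall effect. At stake is how the subgroup tables are read, including any later discussion of consistency by region, serostatus, age or weight.

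**Working it through.** **Inputs.** ACR20 rates of 62% on MTX alone and 78% on each filgotinib group, and arms of 400, 200, 200 and 400 (SAP 1.3). Two-sided 0.05 (SAP 3). *Assumption:* the subgroup shares, since the documents give no counts. A share s of a 400-patient arm is 400s, and of a 200-patient arm 200s.

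**Step 1: reproduce the plan's figure.** The usual two-proportion formula for 62% vs 78% gives power of 99.9% at 400 vs 400 and 98.3% at 400 vs 200. The stated figure of over 90% holds. Fisher's test gives 99.8% and 98.1%.

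**Step 2: the same effect inside a subgroup.** Exact Fisher power is the sum, over all pairs (x, y), of Bin(x; n₀, 0.62) × Bin(y; n₁, 0.78), counting the pairs with Fisher p ≤ 0.05. Column heads give the full arms compared, MTX alone first; the pair in each cell is MTX vs filgotinib within the subgroup.

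| Assumed share | 400 vs 400 arms | 400 vs 200 arms |
|---|---|---|
| 10% | 40 vs 40: 26% | 40 vs 20: 19% |
| 20% | 80 vs 80: 54% | 80 vs 40: 41% |
| 30% | 120 vs 120: 73% | 120 vs 60: 58% |
| 50% | 200 vs 200: 93% | 200 vs 100: 80% |

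**Step 3: how often the levels appear to disagree.** For a two-level factor in the 400-patient arms, the levels contain different patients, so P(large level significant, small level not) = power(large) × (1 − power(small)):

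- 10/90 split: 0.996 × (1 − 0.263) = 0.73
- 20/80 split: 0.992 × (1 − 0.536) = 0.46
- 30/70 split: 0.983 × (1 − 0.735) = 0.26

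With the same common effect, a Wald interaction test on the risk-difference scale rejects in 5.6% (10/90) and 5.2% (20/80) of 200,000 simulated trials.

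**Step 4: how much of this is due to Fisher's test?** Enumerate the same cases with an unpooled normal-approximation 95% CI for the difference, and count the trials in which it excludes zero.

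| Sizes | Fisher p ≤ 0.05 | CI excludes zero |
|---|---|---|
| 80 vs 80 | 54% | 61% |
| 40 vs 80 | 41% | 48% |
| 40 vs 40 | 26% | 36% |
| 20 vs 40 | 19% | 31% |

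In the three smaller cases most intervals still cross zero, so size is the main cause.

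**Step 5: what the missing interval would show.** Take 25/40 on MTX and 31/40 on filgotinib. Fisher p = 0.22. The difference is 0.775 − 0.625 = 0.150, with SE = √(0.625×0.375/40 + 0.775×0.225/40) = 0.101. The 95% CI is 0.150 ± 1.96 × 0.101, about −5 to 35 points. It includes both zero and the planned 16 points, so the data are inconclusive. The p-value alone does not convey that.

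**The case against.** **No decision rule.** The SAP nowhere says that a subgroup effect is present or absent according to p < 0.05, and it claims neither heterogeneity nor consistency. This stands. A reader might infer that the plan judges subgroups by significance or will report small ones as failures, but the text does not say so. The point is limited to which outputs are planned.

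**The difference can be recovered.** Counts and percentages per arm are reported, so anyone can subtract and form a crude interval. This is true, but nothing prespecifies the interval or its method, and the SAP does prespecify one for the continuous endpoints.

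**The power loss is mostly size.** Step 4 confirms this. A reader might infer that changing the test would rescue small subgroups; it would not.

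**The sizes are guesses.** No document gives counts for patients aged 65 or over, seronegative patients or Japan, so none of these can be called small on the documents alone. SAP 6.5 does report low enrolment in some combinations of the stratification factors, but that concerns combinations and not single subgroup levels. For a level with half the patients, power is 80% to 93% and the problem is small.

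**Fisher's test is defensible in sparse tables.** It is, which is a reason to keep it as a supplement and to choose the interval method with care.

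**Interaction tests are weak.** If the small level had no effect (62% vs 62%) and the large level had the planned 16 points, a risk-difference interaction test in the 400-patient arms would have about 29% power at a 10% share and 47% at 20% (normal approximation). A non-significant interaction therefore does not establish consistency.

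**Conclusion.** The point holds as a gap in the planned subgroup output for ACR20 and DAS28(CRP) < 2.6. Within-level Fisher p-values do not address whether the effect differs between levels, and no estimate with an interval accompanies them, contrary to the SAP's own practice elsewhere. Under a common effect of 62% vs 78%, a significant large level beside a non-significant small one would occur in about 73% of trials at a 10/90 split and 46% at 20/80 in the 400-patient arms.

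These figures rest on assumed subgroup shares and on the planned ACR20 rates. The documents give no DAS28(CRP) < 2.6 rates, so the size is shown for ACR20 only, although the mechanism is the same.

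A reader might infer that type I error control or the primary claim is weakened. The documents do not support that: no subgroup enters the testing sequence in SAP 3.5, so the confirmatory conclusions are unaffected. This is a cheap improvement to reporting.

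**What to change.** In SAP 6.2.5 and 6.3.4:

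1. For each subgroup level and each filgotinib-vs-MTX comparison, add the response-rate difference with a 95% CI by a named method suited to small cells, such as Newcombe or Miettinen-Nurminen. Fisher's p-value may stay as a supplement.
2. Add one treatment-by-subgroup interaction p-value per factor and comparison from the planned logistic model. State that it is on the odds-ratio scale, because it can disagree with a comparison of rate differences when control rates vary between levels. Prespecify that sparse levels are pooled or omitted.
3. For the continuous key secondary endpoints, add the matching interaction at Week 24 in the MMRM.
4. Label all of this exploratory and say that a non-significant interaction is not evidence of consistency.

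The cost is a little programming. With ten factors and three comparisons there would be 10 × 3 = 30 interaction p-values per endpoint, beside at least 22 × 3 = 66 within-level p-values before race is counted. The downside is the low power of interaction tests. No confirmatory test, sample size or data collection changes.

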### 6.3. Key Secondary Efficacy Endpoints

The key secondary efficacy endpoints are:

- Change from Baseline in the HAQ-DI score at Week 24
- Change from Baseline in the mTSS at Week 24
- Proportion of subjects who achieve DAS28(CRP) < 2.6 at Week 24
- Change from Baseline in SF-36 PCS at Week 24
- Change from Baseline in FACIT-Fatigue at Week 24

### 6.3.1. Definition of Key Secondary Efficacy Endpoints

#### 6.3.1.1. Modified Total Sharp Score (mTSS)

Subject's radiographs of bilateral hands, wrists and feet will be taken at screening and protocol specified visits. The radiographs will be evaluated through central review by independent joint assessors using the mTSS method. The mTSS (range [0, 448]) is defined as the erosion score (range [0, 280]) plus the joint space narrowing (JSN) score (range [0, 168]). The change in erosion score, JSN score and mTSS will be computed for each patient at scheduled visits as the following:

$$\text{change in score} = \text{postbaseline score} - \text{baseline score}$$

For the missing joint score (regardless of reasons of missing), if at least half of the joints are assessed for hand joints erosion, foot joints erosion, and JSN, respectively, at a given visit, the total scores for the afore mentioned joints will be prorated using the following formula:

$$\text{Hand joints erosion score} = \frac{\text{total score among available hand joints}}{\text{sum of weights among the available hand joints}} \times 160$$

$$\text{Foot joints erosion score} = \frac{\text{total score among available foot joints}}{\text{sum of weights among the available foot joints}} \times 120$$

$$\text{JSN score} = \frac{\text{total score among available joints}}{\text{sum of weights among the available joints}} \times 168$$

The weight is defined as the possible maximum score of each joint.

If any of the hand joints erosion, foot joints erosion, or JSN has more than half of the joints not evaluable at a given visit, the mTSS will be treated as missing for that visit.

Detailed algorithm for calculating mTSS is described in [Appendix 4](#).

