## 1.2. Study Design

[figure not shown]
This is a randomized, double-blind, placebo- and active-controlled, add-on, Phase 3 study in adult male and female subjects with moderately to severely active RA who have limited or no prior exposure to MTX therapy. The study is designed to evaluate the efficacy, safety and tolerability of filgotinib as well as its effect on patient-reported outcomes, including work productivity, fatigue, and quality of life. In addition, PK will be assessed.

Approximately 1200 subjects will be randomized in a 2:1:1:2 ratio to filgotinib 200 mg plus MTX, filgotinib 100 mg plus MTX, filgotinib 200 mg alone, or MTX alone, for up to 52 weeks:

- Filgotinib 200 mg + MTX group: filgotinib (200 mg once daily [q.d.]) + PTM filgotinib 100 mg (PTM q.d.) + MTX (once weekly up to 20 mg) (N=400)
- Filgotinib 100 mg + MTX group: filgotinib (100 mg q.d.) + PTM filgotinib 200 mg (PTM q.d.) + MTX (once weekly up to 20 mg) (N=200)
- Filgotinib 200 mg monotherapy group: filgotinib (200 mg q.d.) + PTM filgotinib 100 mg (PTM q.d.) + PTM MTX (PTM once weekly) (N=200)
- MTX monotherapy group: PTM filgotinib 100 mg (PTM q.d.) and PTM filgotinib 200 mg (PTM q.d.) + MTX (once weekly up to 20 mg) (N=400)

Randomization will be stratified by geographic region and presence of rheumatoid factor (RF) or anti-cyclic citrullinated peptide antibody (anti-CCP Ab) at screening.

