### 1.3. Sample Size and Power

Sample size is determined based on the superiority test of filgotinib in combination with MTX compared to MTX alone based on the change from Baseline in mTSS at Week 24. When assuming a difference of 0.62 between the two groups and a common standard deviation of 2.7, 400 subjects in the filgotinib 200 mg in combination with MTX group and 400 in the MTX alone group are required to obtain 90% power at a 2-sided 0.05-level.

The total sample size will be 1200 (400 subjects for filgotinib 200 mg in combination with MTX group, 200 subjects for filgotinib 100 mg in combination with MTX group, 200 subjects for filgotinib 200 mg alone group and 400 subjects for MTX alone group). This sample size will provide over 90% power to detect an increase in ACR20 response rate of 62% to 78% between the MTX alone group and each of the filgotinib groups respectively, using a 2-sided 0.05-level test.

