#### **6.4. Other Secondary Efficacy Endpoints**

Other secondary efficacy endpoints include:

- Change from Baseline in the mTSS at Week 52
- The proportion of subjects who achieve ACR50 and ACR70 at Weeks 4, 12, 24, and 52, ACR20 at Weeks 4, 12, and 52, and ACR20/50/70 over time from Day 1 through Week 52
- Change from Baseline in individual components of the ACR response at Weeks 4, 12 and 24, and 52 and over time from Day 1 through Week 52
- The proportion of subjects who achieve change (ie, decrease) in HAQ-DI of  $\geq 0.22$  at Weeks 4, 12, 24, and 52, and over time from Day 1 through Week 52
- Change from Baseline in DAS28(CRP) at Weeks 4, 12, 24, and 52, and over time from Day 1 through Week 52
- The proportion of subjects who achieve DAS28(CRP)  $\leq 3.2$  at Weeks 4, 12, 24, and 52, and over time from Day 1 through Week 52
- The proportion of subjects who achieve DAS28(CRP) < 2.6 at Weeks 4, 12, and 52, and over time from Day 1 through Week 52
- ACR-N and European League Against Rheumatism (EULAR) response at Weeks 4, 12, 24 and 52, and over time from Day 1 through Week 52
- Change from Baseline in CDAI at Weeks 4, 12, 24, and 52, and over time from Day 1 through Week 52

- Change from Baseline in SDAI at Weeks 4, 12, 24, and 52, and over time from Day 1 through Week 52
- The proportion of subjects who had no radiographic progression from Baseline (applying threshold of 0.5 on change from baseline in mTSS) at Week 24 and 52
- Absolute value and change from Baseline in SF-36, FACIT-Fatigue, and the EQ-5D over time at Weeks 4, 12, 24, and 52, and over time from Day 1 through Week 52
- Absolute value and change from Baseline in WPAI-RA at Weeks 4, 12, 24, and 52, and over time from Day 1 through Week 52

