## Appendix 4. Modified Total Sharp Score

### Modified Sharp Method

The joint erosion score is a summary of erosion severity in 32 joints of the hands and 12 joints in the feet, as shown below for the joints assessed for erosions.

Hands/Fingers MCP: Metacarpophalangeal joints I - V (n = 10)	Hands/Wrist: Multangular bones(trapezium & trapezoid) (n = 2)
Hands/Fingers PIP: Proximal interphalangeal joints II - V (n = 8)	Hands/Wrist: Scaphoid(Navicular) bones (n = 2)
Hands/Fingers IP (thumbs): Interphalangeal joints (n = 2)	Hands/Wrist: Lunate bones (n=2)
Hands/Fingers (thumbs): Proximal Metacarpal joints (n = 2)	Feet/Toes MTP: Metatarsophalangeal joints I – V (n = 10)
Hands/Wrist: Distal Radius (n = 2)	Feet/Toes IP (big toes): Interphalangeal joints (n = 2)
Hands/Wrist: Distal Ulna (n = 2)	

An erosion score of 0 to 5 is given to each joint in the hands and wrists, and a score of 0 to 10 is given to each joint in the feet. Each hand and wrist joint is scored, according to the surface area involved, from 0 to 5, with 5 indicating extensive loss of bone from more than one half of the articulating bone (0 indicates no erosion). Because each side of a foot joint is graded on this scale, the maximum erosion score for a foot joint is 10. Thus, the maximum erosion score for hands and wrists is  $32*5 + 12*10 = 280$ . A joint may not be evaluable due to surgery (i.e., joint replacement) or may be radiographically insufficient for reading.

The joint space narrowing (JSN) score summarizes the severity of JSN in 30 joints of the hands/wrists and 12 joints of the feet, as shown below for the joints assessed for JSN.

Hand/Fingers MCP: Metacarpophalangeal joints I – V (n = 10)	Hand/Wrist: Capitate-scaphoid Joint (n = 2)
Hand/Fingers PIP: Proximal interphalangeal joints II - V (n = 8)	Hand/Wrist: Scaphoid-radius Joint (n=2)
Hand/Fingers CMC: Carpometacarpal joints III, IV, V (n = 6)	Foot/Toes MTP: Metatarsophalangeal joints (n = 10)
Hand/Wrist: Scaphoid-Trapezium Joint (n = 2)	Foot/Toes IP: Interphalangeal joints (n = 2)

Assessment of JSN for each hand (15 joints per hand) and foot (6 joints per foot), including subluxation, is scored from 0 to 4, with 0 indicating no/normal JSN and 4 indicating complete loss of joint space, bony ankylosis, or luxation. Thus, the maximal JSN score is  $(30*4) + (12*4) = 168$ . A joint may not be evaluable due to subluxation, luxations, surgery (i.e., joint replacement) or may be radiographically insufficient for reading.

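### mTSS components are prorated separately at each visit, so a joint readable at only one visit can give a stable patient a spurious change; taking change over common joints is a cheap improvement

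*SAP*

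**What the plan says.** SAP 6.3.1.1 builds mTSS from three prorated components: hand erosion, foot erosion and joint space narrowing (JSN). Proration applies "if at least half of the joints are assessed for hand joints erosion, foot joints erosion, and JSN, respectively, at a given visit". The total over the available joints is divided by the sum of their maximum scores and multiplied by the component maximum, whatever the reason a joint is missing. The section also states: "The change in erosion score, JSN score and mTSS will be computed for each patient at scheduled visits as the following", followed by post-baseline minus baseline.

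Appendix 4, to which 6.3.1.1 refers for the detailed algorithm, says of erosion: "A joint may not be evaluable due to surgery (i.e., joint replacement) or may be radiographically insufficient for reading". For JSN it adds subluxation and luxation to that list. Some of these causes can arise between two visits. Neither section requires the two visits to share a joint set, and neither carries a joint score from one visit to another.

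Change in mTSS at Week 24 is tested fourth, fifth and eleventh in the hierarchy of SAP 3.5. It also drives the sample size in SAP 1.3: "When assuming a difference of 0.62 between the two groups and a common standard deviation of 2.7". SAP 6.4 classifies patients as free of radiographic progression by "applying threshold of 0.5 on change from baseline in mTSS", and SAP 6.4.2 repeats that analysis at thresholds of 0 and the smallest detectable change.

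**The concern.** Under this rule the baseline and Week 24 totals of one patient can rest on different joints. Their difference then mixes true progression with a change in the joint set. If an undamaged joint drops out at follow-up, the remaining damage is scaled up and the patient appears to worsen. If a damaged joint drops out, its score is replaced by the average of the others and the patient appears to improve. The signs reverse when the joint is unreadable at baseline only.

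At stake are added noise in a key secondary endpoint, misclassification against the no-progression thresholds and, if unreadability is related to arm or to outcome, bias in the treatment difference. No planned analysis would show it. The multiple imputation and tipping-point analyses in SAP 6.3.3.2 act on missing endpoint values, not on prorated ones. The per-protocol analysis reuses the same score. SAP 3.6.2 plans no sensitivity analysis for outliers.

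**Working it through.** **Inputs from the documents.** Component maxima M and joint weights w (SAP Appendix 4): hand erosion 32 × 5 = 160, w = 5; foot erosion 12 × 10 = 120, w = 10; JSN 42 × 4 = 168, w = 4. Sizing (SAP 1.3): difference 0.62, SD 2.7, "400 subjects in the filgotinib 200 mg in combination with MTX group and 400 in the MTX alone group", which "are required to obtain 90% power at a 2-sided 0.05-level".

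**Assumptions.** Joint totals, the score of the lost joint and the share of patients affected. None of these is in the documents.

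**1. The plan's own figure.** n = 2(1.960 + 1.282)² × 2.7² / 0.62² gives 399 per group. The t-test version gives 399.5, that is 400. Power at 400 is 90.1%. The stated size reproduces.

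**2. False change in a stable patient.** Let one joint with score s be unreadable at follow-up only, and let the other joints of the component total R. Baseline is R + s and follow-up is R × M/(M − w), so

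false change = R × w/(M − w) − s.

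The multiplier w/(M − w) is 5/155 = 0.0323 (hand), 10/110 = 0.0909 (foot) and 4/164 = 0.0244 (JSN).

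| Component | Lost joint's score s | Others' total R | False change |
|---|---|---|---|
| Hand erosion | 0 | 0 | 0 |
| Hand erosion | 0 | 5 | +0.16 |
| Hand erosion | 0 | 10 | +0.32 |
| Hand erosion | 0 | 20 | +0.65 |
| Foot erosion | 0 | 5 | +0.45 |
| Foot erosion | 0 | 10 | +0.91 |
| JSN | 0 | 10 | +0.24 |
| JSN | 0 | 30 | +0.73 |
| Hand erosion | 1 | 5 | -0.84 |
| Hand erosion | 1 | 30 | -0.03 |
| Hand erosion | 5 | 35 (total 40) | -3.87 |

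For k zero-score hand joints lost together, the false change is R × 5k/(160 − 5k). With R = 10 this is +0.67 for k = 2 and +1.43 for k = 4; with R = 20 it is +1.33 and +2.86.

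**3. Against the patient-level thresholds.** One lost zero-score joint reaches 0.5 when R is at least 0.5 × 155/5 = 15.5 (hand), 0.5 × 110/10 = 5.5 (foot) or 0.5 × 164/4 = 20.5 (JSN). At the threshold of 0, any damage elsewhere in that component is enough.

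**4. At group level, error unrelated to arm.** Take a share p of patients with error size e, averaging to zero: SD = √(2.7² + p × e²).
- p = 5%, e = 0.62: SD 2.70, power 90.0%.
- p = 20%, e = 1.0: SD 2.74, power 89.3%.
- p = 20%, e = 3: SD 3.02, power about 83%.

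**5. At group level, error related to arm.** If one arm has an excess of 5% to 20% of patients with a same-direction error of 0.62 to 1.0, the mean difference shifts by 0.05 × 0.62 = 0.03 to 0.20 × 1.0 = 0.20. That is 5% to 32% of 0.62.

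**6. With matched joints.** For R = 10 and one hand joint lost, both visits give 10 × 160/155, so the false change is exactly 0.

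**7. Luxation.** Suppose a JSN joint scored 3 at baseline luxates and the other JSN scores total 10. Scored 4, as Appendix 4 allows, it contributes +1. Called not evaluable, as Appendix 4 also allows, the prorated change is 10 × 4/164 − 3 = -2.76. Under matching it contributes 0.

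**The case against.** The strongest case for the plan is that the rule is prespecified, complete and internally consistent, and that matched joints are a different convention rather than the correction of a mistake. SAP 6.1.1 uses the same half-of-joints proration for tender and swollen counts. Protocol 4.3 excludes planned major surgery during the study and prior surgical treatment for RA in more than 4 joints, which narrows the joint-replacement route. Protocol 3.2 provides for repeat screening radiographs, and Protocol 6.7.1.11 has two independent blinded readers. Nothing suggests that film quality differs by arm. The no-progression endpoint lies outside the hierarchy and carries nominal p-values only.

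Most of this stands, and it limits the point to an improvement. It does not remove the mechanism. Film quality and luxation remain as causes after baseline, and blinded reading does not stop a joint from being unreadable at one visit only. The comparison with joint counts is incomplete, because Protocol Appendix 7 omits joints not assessable at screening from all later counts and the radiographs have no such rule.

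There are also objections to matching itself. Baseline mTSS is a covariate in the MMRM and would become visit-specific; keeping the full prorated baseline as the covariate avoids this. A joint lost to luxation would drop out of both visits, so its true progression is lost; but it then contributes zero rather than a false improvement. An imaging charter, not among the documents, may already hold a matching rule. If so, SAP 6.3.1.1 should cite it.

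**Conclusion.** The concern holds in a limited form. Visit-by-visit proration can give a stable patient a non-zero change of either sign, and a common joint set removes it. The size depends on the lost joint's score and on the other damage. It is zero for an undamaged joint in a component with no other damage, and near zero when the lost joint is of average score.

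A reader might infer that a single unreadable joint manufactures an effect as large as the 0.62 on which the trial is sized. The documents do not support that. The 0.62 is a difference between group means, and the artefact is one patient's error. It would move the estimate by 0.62 only if errors averaged 0.62 across one arm relative to the other. The fair patient-level comparators are the no-progression thresholds of 0.5 and 0 and the SD of 2.7. Nor do the documents show that the rule is an error, that the 400 per group is wrong, or that the arms differ in readability.

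If unrelated to arm, the effect is mainly noise, with power at about 89% to 90% under the moderate assumptions above. Bias needs unreadability that differs by arm or depends on outcome. The luxation wording in Appendix 4 leaves the second possible. How much this matters rests on baseline damage and on how often joints are unreadable, and neither is given. The change is a cheap improvement.

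**What to change.** In SAP 6.3.1.1:
- Compute each change from joints evaluable at both baseline and that visit, prorate both totals by the same weight sum, and apply the half-of-joints rule to the common joints.
- Keep the full prorated baseline mTSS as the MMRM covariate.
- Report by arm the number of joints readable at only one of the two visits.
- Keep the current per-visit proration as a sensitivity analysis. At minimum, prespecify the matched-joint change as the sensitivity analysis instead.

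In Appendix 4, reconcile the JSN sentence that gives luxation a score of 4 with the sentence that lists luxation and subluxation as reasons a joint may not be evaluable.

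The cost is one sentence on the calculation, one on reporting and a small program change, made before the Week 24 unblinding. There are two downsides. A few changes may become missing under the common-joint half rule, and the baseline total entering a change may differ slightly between the Week 24 and Week 52 comparisons. The sample size is unaffected.
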